# 4.1.2 **Duration of Study**

The expected duration of each patient's participation in the study will be up to 18 months.

# 5 SELECTION AND WITHDRAWAL OF PATIENTS

Investigator(s) will record who sign the informed consent form for entry into the study.

Each patient should meet all of the inclusion criteria and none of the exclusion criteria for this study.

Protocol No.: TEN-02-401

Edition No.: 1

#### 5.1 Inclusion Criteria

A patient will be eligible for study participation if he/she meets the following criteria:

- 1. Signed and dated informed consent prior to any study specific procedures.
- 2. Completion of TEN-02-301 (Visit 23).
- 3. Women must be non-pregnant, non-lactating and fulfilling one of the following:
  - a. Post menopausal defined as amenorrhea for at least 12 months following cessation of all exogenous hormonal treatments and with follicle stimulating hormone (FSH) levels in the laboratory defined post-menopausal range (from TEN-02-301 study), or 60 years of age or greater..
  - b. Documentation of irreversible surgical sterilization by hysterectomy, bilateral oophorectomy or bilateral salpingectomy, but not tubal ligation.
  - c. Use of acceptable contraceptive method: IUD with spermicide, a female condom with spermicide, contraceptive sponge with spermicide, an intravaginal system (e.g., NuvaRing®), a diaphragm with spermicide, a cervical cap with spermicide, or oral, implantable, transdermal, or injectable contraceptives, sexual abstinence, or a sterile sexual partner.
  - d. Male partner who is sterile or using a condom with spermicide.
- 4. Male participants must agree to avoid fathering a child (or donating sperm), and therefore be either sterile (documented) or agree to use, from the time of enrollment until 30 days after end of study, one of the following approved methods of contraception: a male condom with spermicide, a sterile sexual partner, use of an IUD with spermicide by female sexual partner, a female condom with spermicide, contraceptive sponge with spermicide, an intravaginal system (e.g., NuvaRing®), a diaphragm with spermicide, a cervical cap with spermicide, or oral, implantable, transdermal, or injectable contraceptives.
- 5. Able to understand and comply with the protocol.

#### 5.2 Exclusion Criteria

A patient will not be eligible for study participation if he/she meets any of the exclusion criteria, or will be discontinued at the discretion of the Investigator if he/she develops any of the following exclusion criteria during the study:

1. Scheduled for living donor kidney transplant, plans to change to a different method of dialysis, home HD or plans to relocate to another center during the study period.

Protocol No.: TEN-02-401

Edition No.: 1

- 2. Life expectancy <12 months.
- 3. If, in the opinion of the Investigator, the patient is unable or unwilling to fulfill the requirements of the protocol or has a condition which would render the results uninterpretable.

#### 5.3 Patient Withdrawal

Patients are free to discontinue the study at any time, for any reason, and without prejudice to further treatment. The Investigator may remove a patient if, in the Investigator's judgment, continued participation would pose unacceptable risk to the patient or to the integrity of the study data.

A patient who discontinues will always be asked about the reason(s) for discontinuation and the presence of any AEs. The Investigator will record the reason for early withdrawal in the eCRF.

[figure not shown]
If a patient discontinues the study, all visit procedures for Visit 13 (EOT) will be completed, if possible.

# 5.4 Early Termination of Study

The study may be terminated at any time by the Sponsor for reasons including but not limited to the following (i) if serious side effects occur, (ii) if the Investigator does not adhere to the protocol, (iii) if, in the Sponsor's judgment, there are no further benefits to be achieved from the study, or (iv) for administrative reasons. In the event that the clinical development of the investigational product is discontinued, Ardelyx, Inc. shall inform all Investigators / institutions and IRBs overseeing the trial.

# **6 TREATMENT OF PATIENTS**

- 6.1 Administration of Investigational Product
- 6.1.1 Identity of Investigational Product(s)
- 6.1.1.1 Tenapanor

Protocol No.: TEN-02-401

Edition No.: 1

#### 6.1.1.2 Sevelamer

Sevelamer carbonate will be supplied, as commercially available.

#### 6.1.2 Treatments Administered

Tablets containing 10 mg of tenapanor will be taken once or twice daily PO just prior to breakfast and dinner (for QD biggest meal of the day). On dialysis days, patients on HD should **not** take study drug at the meal prior to dialysis and instead take it before another meal. Each dose of one to three tablets will achieve total daily doses between 10mg and 60 mg tenapanor. If a meal is skipped, the dose should be taken with another meal during the day or at around the time that the meal would have been consumed.

Sevelamer should be taken as described in the protocol or in the package insert.

#### 6.1.3 Dose Adjustments

All patients in the tenapanor group will start at the dose that they were receiving at the end of the TEN-02-301 study. Dosing regimens can be adjusted based on the most recent sP laboratory data (central laboratory data or standard of care local laboratory data).

#### **Tenapanor Arm**

The dosing regimens described below for sevelamer are for guidance to the Investigators. Investigators have flexibility to dose sevelamer, TID, BID or QD based on their experience with each patient or as per package insert. Dosing regimens can be adjusted based on the most recent sP laboratory data (central laboratory data or standard of care local laboratory data).

If patients are in the tenapanor arm (from the TEN-02-301 study), sevelamer will be added as described below:

- sP ≥2.5 and ≤4.5 mg/dL: no addition of sevelamer.
- sP >4.5 and ≤5.0 mg/dL: add one 800 mg tablet QD.
- sP >5.0 and ≤5.5 mg/dL: add one 800 mg tablet BID.
- sP >5.5 mg/dL: add one 800 mg tablet TID.

If sP is still greater than or becomes >4.5 mg/dL at a subsequent visit, sevelamer dose can be increased in a stepwise manner as described below:

Protocol No.: TEN-02-401

Edition No.: 1

- sP >4.5 and  $\leq$ 5.0 mg/dL: add one 800 mg tablet to the existing regimen.
- sP > 5.0 and  $\le 5.5$  mg/dL: add two 800 mg tablets to the existing regimen.
- sP >5.5 mg/dL: add three 800 mg tablets each day (800 mg TID) to the existing regimen.

The maximum dose of sevelamer should be based on standard of care, the sevelamer package insert, and the Investigator's experience with each patient.

If sP < 2.5 mg/dL at any visit

- Sevelamer dose can be lowered by one 800 mg tablet TID, or as appropriate, based on current regimen; Investigators have flexibility to dose sevelamer BID or QD based on their experience with each patient or as per package insert.
- If patient is not taking sevelamer then tenapanor dose can be lowered by one 10 mg tablet BID, unless already at tenapanor 10 mg BID, then can dose tenapanor 10 mg QD

#### **Sevelamer Arm**

If patients are from the TEN-02-301 sevelamer arm, tenapanor dose will be added based on their baseline sP as described below. Investigators may decrease or increase the tenapanor dose based on sP levels and/or GI tolerability in 10 mg increments to a minimum of 10 mg QD or a maximum of 30 mg BID, not more than once daily. Dosing regimens can be adjusted based on the most recent sP laboratory data (central laboratory data or standard of care local laboratory data).

- sP >2.5 and ≤3.5 mg/dL: add three 10 mg tablets of tenapanor QD and Sevelamer dose can be lowered by one 800 mg tablet TID.
- sP > 3.5 and  $\leq 4.5$  mg/dL: add three 10 mg tablets of tenapanor QD
- sP >4.5: add three 10 mg tablets of tenapanor BID

If sP >4.5 mg/dL at next visit

 add three 10 mg tenapanor tablets, if on QD regimen to a maximum of 30 mg tenapanor BID. If on 30 mg tenapanor BID follow sevelamer dose regimen changes described below

Sevelamer dose can be increased by at least one 800 mg tablet at the largest meal and up to one 800 mg tablet TID; Investigators have flexibility to dose sevelamer BID or QD based on their experience with each patient or as per package insert. If sP < 2.5 mg/dL at any visit:

Protocol No.: TEN-02-401

Edition No.: 1

Sevelamer dose can be lowered by one 800 mg tablet TID; Investigators have flexibility
to dose sevelamer BID or QD based on their experience with each patient or as per
package insert.

• If patient is not taking sevelamer then tenapanor dose can be lowered by one 10 mg tablet BID, unless already at tenapanor 10 mg BID, then can dose tenapanor 10 mg QD.

#### **6.1.3.1 Discontinuation Criteria**

See Section 5.3 Patient Withdrawal

# 6.1.4 Method of Assigning Patients to Treatment Groups

Patients will enter the TEN-02-401 study into the same group as from the TEN-02-301 study.

# 6.2 Investigational Product Storage and Accountability

# **6.2.1** Storage Conditions

The Investigator will ensure that all the study drugs are stored and dispensed in accordance with Food and Drug Administration (FDA) regulations concerning the storage and administration of investigational drugs.

Tablets of tenapanor should be stored in the original packaging according to the labeling. Sevelamer should also be stored in the original packaging according to the labeling.

#### 6.2.2 Drug Accountability

The Investigator must ensure that all drug supplies are kept in a secure locked area with access limited to those authorized by the Investigator. The Investigator or the Investigator's designee must maintain accurate records of the receipt of all study drug shipped by the Sponsor or its representative, including but not limited to the date received, lot number, expiration date, amount received, and the disposition of all study drug. Current dispensing records will also be maintained, including the date, bottle number (for tenapanor), and amount of study drug dispensed, and the patient receiving the drug, to be recorded both on the Master IP log and Subject IP log. All remaining study drug not required by regulations to be held by the clinical facility must be returned to Sponsor or its representative at the last IMV or the COV using the study drug return form provided.

Protocol No.: TEN-02-401

Edition No.: 1

#### 6.3 Packaging and Labeling

# 6.3.1 Study Drug

Tablets of tenapanor should be stored in the original packaging according to the labeling.

# 6.3.2 Blinding Methods

The study is open labeled and study drug will not be blinded.

#### 6.4 Concomitant Medications

# 6.4.1 Concomitant Therapy

The use of concomitant medications during the study, will only be recorded in this study if it is a major change from the medications used at entry into the TEN-02-401 study.

A major change is defined as the addition of a new drug used to treat a serious adverse event (SAE) or the removal of a drug due to the improvement of a disease/condition (i.e., blood pressure improvement)

# 7 COLLECTION OF STUDY VARIABLES

# 7.1 Recording of Data

The Investigator will ensure that data are recorded in the electronic Case Report Form (eCRF) for this study. The Investigator ensures accuracy, completeness, and timeliness of the data recorded and of the provision of answers to data queries. The Investigator will sign the completed eCRF and a copy of the completed eCRF will be archived.

# 7.2 Data Collection Prior to Enrollment

No baseline assessments will be performed as part of this protocol; all baseline data for TEN-02-401 will be taken from the TEN-02-301 End of Treatment (EOT) visit, if available, and include the following:

- Date of birth, gender, and race
- Weight (pre-dialysis) and height (kg and cm, respectively)
- Kt/V most recent value prior to enrolling into TEN-02-401

Protocol No.: TEN-02-401

Edition No.: 1

- KDQoL survey
- DSI survey (for English speakers only)
- Medical history (major medical conditions taken from TEN-02-301)
- Physical examination
- Vital signs (pre-dialysis)
- Electrocardiogram (ECG) evaluation
- Blood sample for clinical laboratory tests
- Pregnancy test, if applicable
- Blood sample for FGF23 and exploratory biomarkers
- Concomitant medications

#### 7.2.1 Safety Variables

Safety assessments will be performed during the study and will include physical examinations, vital signs, body weights, clinical laboratory tests, electrocardiograms, and adverse event recording. Body weight, vital signs and blood collections for laboratory assessments **must** be performed predialysis. All other assessments may be performed pre-, during, or post-dialysis but should be performed at the same time at each visit. See Section 8 (Methodology/Study Visits) for a detailed schedule of procedures.

# 7.2.2 Physical Examination

The physical examination will include an assessment of the following items: general appearance, skin (including any pitting edema in lower legs / feet), cardiovascular, respiratory, abdomen. Any findings or absence of findings relative to each patient's physical examination will be carefully documented in the patient's eCRF.

# 7.2.3 Vital Signs (blood pressure and heart rate)

Blood pressure and heart rate will be obtained at all patient visits (pre-dialysis). Blood pressure, sitting systolic and diastolic blood pressure (SSBP and SDBP) will be measured after the patient has been sitting for approximately 5 minutes. All measurements will be recorded on the source document and in the eCRF.

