# If sP <2.5 mg/dL at any visit

- Sevelamer dose can be lowered by one 800 mg tablet TID;
   Investigators have flexibility to dose sevelamer BID or QD based on their experience with each patient or as per package insert.
- If patient is not taking sevelamer then tenapanor dose can be lowered by one 10 mg tablet BID, unless already at tenapanor 10 mg BID, then can dose tenapanor 10 mg QD

For all subjects enrolled in TEN-02-401, tenapanor will be taken either once (QD; just prior to dinner or largest meal of the day) or twice daily (BID; just prior to breakfast and dinner. Patients on HD should not take tenapanor at the meal immediately preceding dialysis; in this case, patients will take tenapanor prior to the previous or next meal after dialysis. Sevelamer will be taken as per package insert.

Investigators may decrease or increase the tenapanor dose based on sP levels and/or GI tolerability in 10 mg increments to a minimum of 10 mg BID or a maximum of 30 mg BID not more than once daily.

Laboratory assessments will be measured at every visit (Weeks 1, 2, 3, 4, 6 and 8 and Months 3, 6, 9, 12, 15 and 18) using a central laboratory.

Safety assessments will be performed during the study and will include physical examinations, vital signs (blood pressure and pulse), body weights, clinical laboratory evaluations, 12-lead electrocardiograms (ECGs), and adverse event (AE) monitoring.

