#### 1.3 Schedule of Events

Study Day	Base- line*	W1 ± 2 days	W2 ± 2 days	W3 ± 2 days	W4 ± 2 days	W6 ± 2 days	W8 ± 2 days	M 3 ± 2 weeks	M 4 ± 2 weeks	M 5 ± 2 weeks	M 6 ± 2 weeks	M 7 ± 2 weeks	M 8 ± 2 weeks	M 9 ± 2 weeks	M 10 ± 2 weeks	M 11 ± 2 weeks	M 12 ± 2 weeks	M 13 ± 2 weeks	M 14 ± 2 weeks	M 15 ± 2 weeks	M 16 ± 2 weeks	M 17 ± 2 weeks	M 18 EOT
Visit	V1	V2	V3	V4	V5	V6	V7	V8	T1	T2	V9	T3	T4	V10	T5	T6	V11	T7	T8	V12	Т9	T10	V13
ICF	X																						
I/E Criteria	X																						
Med History m	X																						
BW, Ht, Kt/V1	X							X			X			X			X			X			X
Physical Exam	X																						X
Vital Signs a	X							X			X			X			X			X			X
ECG	X																						X
Clin Lab Tests b	X							X			X			X			X			X			X
Pregnancy Test c	X																						X
Drug Dispense j	X	$X^{j}$	$X^{j}$	$X^{j}$	$X^{j}$	X	$X^{j}$	X			X			X			X			X			
Drug Return k		X	X	X	X	X	X	X			X			X			X			X			X
KDQoL/DSI d	X										X						X						X
s-Phosphorus e	X	X	X	X	X	X	X	X			X			X			X			X			X
FGF23	X							X			X			X			X			X			X
Exploratory Biomarkers f	X							X			X			X			X			X			X
AE Assess g	X	X	X	X	X	X	X	X	X	X	X	X	X	X	X	X	X	X	X	X	X	X	X
ConMedsh	X	X	X	X	X	X	X	X	X	X	X	X	X	X	X	X	X	X	X	X	X	X	X

- \* All baseline procedures, except informed consent and I/E criteria will come from the TEN-02-301 EOT visit; V= visit at office or dialysis center; T= telephone visit;
- W= week, weekly visits are after a short dialysis interval and have a ± window of 2 days; M= month; monthly visits have a ± window of 2 weeks.
- a If collected as part of standard of care, that data can be used and includes blood pressure and pulse.
- b Clinical laboratory tests: All blood collections are performed pre-dialysis.. See Table 7-1 for list of tests.
- c Pregnancy tests (serum) will only be performed on women of child-bearing potential.
- d KDQoL (KDQoLTM-36), Kidney Disease and Quality of Life survey. DSI, Dialysis Symptom Index survey is for English speakers only and is not validated in other languages.
- e Serum phosphorus will be measured by a central laboratory.
- f Serum and plasma samples will be collected at the same time as the clinical laboratory evaluation and sent to the central laboratory for storage.
- g AEs and SAEs will be collected from consenting to the end of study.

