- h Guidelines will be provided to limit the amount of concomitant medication information collected.
- Investigators can adjust doses of tenapanor or sevelamer between visits via telephone. Sevelamer can be re-dispensed at Visits 2, 3, 4, 5, and 8 if dose permits.
- k Sevelamer can be re-dispensed, if enough drug is left until the next visit. Drug accountability is also performed.
- Body weight is for HD patients only, height from TEN-02-301, and Kt/V can be taken from most recent standard-of-care assessment.
- m Major medical conditions taken from TEN-02-301.

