#### 4 STUDY DESIGN

# 4.1 Design Summary

Patients who complete the TEN-02-301 study (PHREEDOM) at Visit 23, may be eligible to enroll into TEN-02-401 (NORMALIZE).

Patients will be required to sign an ICF and meet all inclusion and no exclusion criteria. No baseline assessments will be performed as part of this protocol; all baseline data for TEN-02-401 will be taken from the TEN-02-301 End of Treatment (EOT) visit. Patients from the

Protocol No.: TEN-02-401

Edition No.: 1

TEN-02-301 tenapanor arm will either receive only tenapanor or be given sevelamer in addition to tenapanor based on their sP following a protocol-specified dose titration schedule. Patients from the TEN-02-301 sevelamer arm will be given tenapanor in addition to their sevelamer dose and the sevelamer dose will then be adjusted based on their sP following a protocol-specified dose titration schedule. Patients will be monitored for safety and efficacy with in-office and telephone visits for up to an additional 18 months.

All study visits must be scheduled after a short dialysis interval (only for HD patients; e.g., Wednesday or Friday for patients on a MWF schedule and Thursday or Saturday for patients on a TThS schedule). Body weight and blood collections for laboratory assessments **must** be performed pre-dialysis. All other assessments may be performed pre-, during, or post-dialysis but should be performed at the same time at each visit. For patients receiving PD, visits should be performed on the same day each week, if possible.

Investigators may decrease or increase the dose of tenapanor based on sP levels and/or GI tolerability. The changes must be made in 10 mg increments to a minimum of 10 mg BID or a maximum of 30 mg BID. The dose of sevelamer carbonate may be adjusted based on the guidance provided in Section 4.1.1 or the sevelamer package insert. Investigators have flexibility to dose sevelamer, TID, BID or QD based on their experience with each patient or as per package insert.

Laboratory efficacy endpoints will be assessed at various times throughout the study; sP will be measured at every visit.

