### 8 METHODOLOGY/STUDY VISITS

### 8.1 Baseline, Visit 1

Prior to enrollment, the Investigator will inform each prospective patient of the nature of the study, explain the potential risks, and obtain written informed consent from the patient prior to performing any study-related procedures.

No baseline assessments will be performed as part of this protocol; all baseline data for TEN-02-401 will be taken from the TEN-02-301 End of Treatment (EOT) visit and will consist of the following:

- Informed consent
- Inclusion and exclusion criteria (Section 5)
- Weight (pre-dialysis)
- Kt/V (most recent measurement prior to enrolling into TEN-02-401)
- Medical history (major medical conditions taken from TEN-02-301)
- Phosphate binder used and dose
- KDQoL survey
- DSI survey (for English speakers only)
- Physical examination (Section 7.2.2)
- Vital signs (pre-dialysis) (Section 7.2.3)
- ECG evaluation (Section 7.2.4)
- Clinical laboratory tests (pre-dialysis) (Section 7.2.5)
  - Serum chemistry
  - Hematology
  - o Coagulation profile (if applicable)
- Serum pregnancy test, if applicable
- FGF-23, and exploratory biomarker sample (pre-dialysis)
- Dispense study drug

Protocol No.: TEN-02-401

Edition No.: 1

- Begin collecting adverse events
- Review concurrent medications

# 8.2 Weeks 1, 2, 3, 4, 6, and 8, Visits 2, 3, 4, 5, 6, and 7

- Serum phosphorus (pre-dialysis)
- Return/accountability of study drug
- Dispense study drug
- Adverse event reporting
- Review concurrent medications

# 8.3 Months 3, 6, 9, 12, and 15, Visits 8, 9, 10, 11, and 12

- Weight (pre-dialysis)
- Kt/V (most recent measurement prior to screening)
- KDQoL survey (not Months 9 and 15, Visits 10 and 12)
- DSI survey, for English speakers only (not Months 9 and 15, Visits 10 and 12)
- Vital signs (pre-dialysis) (Section 7.2.3)
- Clinical laboratory tests (pre-dialysis) (Section 7.2.5)
  - Serum chemistry
  - o Hematology
  - o Coagulation profile (if applicable)
- FGF-23, and exploratory biomarker sample (pre-dialysis)
- Return/accountability of study drug
- Dispense study drug
- Adverse event reporting
- Review concurrent medications

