#### 8.8 Total Blood Volume Required for Study

**Table 8-1:** Approximate Blood Volume per Completed Patient

Test	No. of Samples	Volume (mL)	Total (mL)
Hematology (blood)	7	3	21
Chemistry (serum) (includes serum pregnancy test)	7	7	49
Phosphorus (serum)#	6	5	30
iFGF-23 (plasma)	7	4	28
Exploratory biomarker sample (serum and plasma)	7	13	91
Coagulation (plasma)	7	3	21
Total Volume			240

# Separate sample is only taken at specified times when no chemistry sample is taken

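### Section 7.2.3 asks for blood pressure and heart rate at every visit, but the schedule has none at Weeks 1 to 8, when former sevelamer-arm patients start tenapanor

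*Combined protocol and SAP*

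**What the plan says.** Section 7.2.3 sets the rule for vital signs without qualification: "Blood pressure and heart rate will be obtained at all patient visits (pre-dialysis".

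The Schedule of Events in Section 1.3 marks the vital-signs row at baseline and at Months 3, 6, 9, 12, 15 and 18, and leaves Weeks 1 to 8 blank. Footnote a to that row adds: "If collected as part of standard of care, that data can be used and includes blood pressure and pulse". The footnotes also say that "monthly visits have a ± window of 2 weeks".

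Section 8.2, which covers the six weekly visits, names one measurement, "Serum phosphorus (pre-dialysis"). Its other items are drug return and dispensing, adverse events and concurrent medication. Vital signs first reappear in Section 8.3, at Month 3. Section 7.2.1 points to Section 8 for the detailed schedule, and Section 4.1 points to Section 1.3.

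On laboratory tests, the synopsis says "Laboratory assessments will be measured at every visit" and lists the weekly visits among them. Section 4.1 is narrower: "Laboratory efficacy endpoints will be assessed at various times throughout the study; sP will be measured at every visit".

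Section 6.1.3 has former sevelamer-arm patients add tenapanor at entry. Tenapanor-arm patients continue the dose they had at the end of TEN-02-301. Section 2.5 includes lower blood pressure among the theoretical effects of tenapanor, and counts vital signs among the measures that mitigate risk.

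**The concern.** Two parts of the protocol give different instructions for the same visits. A site cannot satisfy Section 7.2.3 by doing only what Sections 1.3 and 8.2 list.

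The timing is what makes this more than a wording slip. The six visits concerned are the first on-treatment visits for patients who come from the sevelamer arm and are new to tenapanor. Section 2.5 relies on vital signs as a safeguard, yet under the schedule that safeguard is not applied while the drug is started and its dose raised. Section 2.5 does note that haemodialysis patients have their health status checked at each dialysis session. It says nothing equivalent for peritoneal dialysis patients, who are also enrolled. At stake is whether any systematic early blood pressure reading exists for new starters who stay in the study.

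**Working it through.** **1. The instructions side by side**

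| Source | Vital signs at Weeks 1, 2, 3, 4, 6, 8 | Vital signs at Months 3, 6, 9, 12, 15, 18 |
|---|---|---|
| Section 7.2.3 | Yes (all patient visits) | Yes |
| Section 1.3, vital-signs row | No | Yes |
| Section 8.2 (weekly visits) | Not listed | n/a |
| Sections 8.3 and 8.5 | n/a | Listed |

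The ten telephone contacts cannot include a blood pressure reading, so only on-site visits are counted.

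**2. Count of visits in conflict**

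Post-baseline on-site visits are Visits 2 to 13, which is 12. Visits 2 to 7 have no scheduled vital signs, which is 6. 6/12 = 50%. With baseline included, 7 of 13 on-site visits have vital signs scheduled and 6 do not.

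**3. Time to the first post-baseline reading**

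- Under Section 7.2.3: Week 1, day 7 ± 2 = day 5 to 9.
- Under the schedule: Month 3 ± 14 days. The protocol gives no day count for a month, so both usual conventions are shown.
  - Month 3 as 12 weeks: 84 ± 14 = day 70 to 98 (10 to 14 weeks).
  - Month 3 as 13 weeks: 91 ± 14 = day 77 to 105 (11 to 15 weeks).
- Nominal delay between the two instructions: 84 − 7 = 77 days, or 91 − 7 = 84 days.

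**4. Exposure during that time**

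Under Section 6.1.3, a former sevelamer-arm patient with baseline phosphorus above 4.5 mg/dL starts tenapanor 30 mg BID. One above 2.5 and up to 4.5 mg/dL starts 30 mg QD, and goes to 30 mg BID if phosphorus exceeds 4.5 mg/dL at the next visit. No starting dose is given for values of 2.5 mg/dL or below. Time on 30 mg BID before the first scheduled reading is therefore:

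- started on BID at day 0: 70 to 105 days across both conventions;
- stepped up at Week 1: from 70 − 9 = 61 days to 105 − 5 = 100 days.

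**5. Are weight and chemistry part of the conflict?**

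No. Table 8-1 in Section 8.8 can be reproduced: 7×3 + 7×7 + 6×5 + 7×4 + 7×13 + 7×3 = 21 + 49 + 30 + 28 + 91 + 21 = 240 mL, as printed. Its 7 chemistry samples are baseline plus Months 3, 6, 9, 12, 15 and 18. Its 6 separate phosphorus samples match the six weekly visits. The table note explains why: "Separate sample is only taken at specified times when no chemistry sample is taken". The phosphorus-only draws are thus deliberate. For weight, Section 1.3 says only that "Body weight is for HD patients only", and no section asks for it at every visit.

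**6. Size of the added work**

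Six extra vital-sign sets per patient. If all 150 to 200 patients attended every visit: 6 × 150 = 900 to 6 × 200 = 1,200 sets. This is an upper bound because some patients will leave early. The protocol gives no split by former arm, so the total for new starters alone cannot be computed.

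**The case against.** The strongest reply is that the protocol shows which text governs. Sections 7.2.1 and 4.1 direct the reader to Sections 8 and 1.3, and these agree with each other on vital signs. On that view the phrase in Section 7.2.3 is a stray, and rewording it would be enough. Safety cover also does not stop: adverse events are asked about at all six visits, Section 8.6 allows unscheduled safety visits, Sections 5.3 and 8.7 call for end-of-treatment procedures on withdrawal, and haemodialysis patients are seen three times a week.

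Much of this stands. Sites probably will follow the schedule, and early clinical events can be captured. But no rule of precedence is stated, so the text needs correcting in any case. If the schedule governs, new starters who remain in the study have no planned early reading. Footnote a does not help as written, because the row it qualifies has no entries at Weeks 1 to 8.

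A reader might infer more than the documents support:

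- **Weight and a chemistry panel are wrongly missing at Weeks 1 to 8.** No section clearly requires them there. The synopsis sentence is loose, and Section 4.1 limits testing at every visit to phosphorus. Adding them is a choice about monitoring intensity.
- **The by-visit safety tables will be empty for Weeks 1 to 8, or sites will produce unequal data.** This depends on the case report form and on the separate SAP that Section 9.1 says governs. Neither is in the document. Phosphorus, itself a listed chemistry test, is measured at all six visits.
- **A site that follows the schedule commits six deviations per patient.** Section 8.9 also refers to the time frame the protocol specifies, and Sections 1.3 and 8 supply one. That reading is strained.

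**Conclusion.** The contradiction on vital signs is real and affects 6 of 12 post-baseline on-site visits. If sites follow the schedule, as is likely, the first planned blood pressure after baseline comes about 10 to 15 weeks after entry. For former sevelamer-arm patients that spans the start of tenapanor and its early titration, although the protocol itself names lower blood pressure as a risk and vital signs as mitigation. Tenapanor-arm patients are continuing a dose they already take, so the point matters mainly for the new starters.

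The range rests on taking Month 3 as 12 or 13 weeks and on the ± 2 week window. The number of patients affected and the rate of events cannot be estimated, since the document gives neither an arm split nor event rates. The consequence is limited by adverse-event questioning, unscheduled visits, withdrawal procedures and, for haemodialysis patients, routine care. This is a gap in planned early safety measurement that is cheap to close. It does not show that early safety would go unobserved.

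**What to change.** 1. In Sections 1.3 and 8.2, mark pre-dialysis blood pressure and heart rate at Weeks 1, 2, 3, 4, 6 and 8, at minimum for patients newly starting tenapanor. Accept standard-of-care values at these visits under footnote a.
2. If the sponsor limits this to new starters, or keeps the present schedule, reword Section 7.2.3 so that it refers to the visits marked in Section 1.3.
3. Align the synopsis sentence: serum phosphorus at every on-site visit, and the other laboratory tests at Months 3, 6, 9, 12, 15 and 18.

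No new visits are needed. The cost is a few minutes and some data entry at six existing visits: six vital-sign sets per patient covered, at most 900 to 1,200 over the study if all patients are included, with less new measurement where routine values are used. Pre-dialysis blood pressure is an imperfect marker of fluid loss, so adverse-event questioning stays necessary.

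Weight and chemistry at Weeks 1 to 8 are optional. If the sponsor wants chemistry, replacing the 5 mL phosphorus sample with the 7 mL chemistry sample at all six visits adds 6 × (7 − 5) = 12 mL, taking Table 8-1 from 240 to 252 mL. The synopsis wording in item 3 would then need to match.
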